7.6.1.1 Adverse Events of Special Importance

Adverse events of peripheral neuropathy, infusion related reactions, immune-related AEs, and other rare serious AEs may be considered AEs of special importance.

Resolution of selected adverse events will be defined as event status of recovered/resolved or recovered/resolved with sequelae; or return to baseline or lower severity as of the latest assessment for pre-existing events. The date of resolution is defined as follows: for events with an onset after the first dose date, if event outcome is "recovered/resolved" or "recovered/resolved with sequelae", then the date of resolution is the event end date; for events ongoing at baseline, if event severity returns to baseline severity or lower as of the last recorded severity, then the date of resolution is the date of severity change to baseline or lower severity.

For events that are not resolved, improvement is defined as decrease by at least one grade from worst grade as of the latest assessment. The date of improvement is defined as follows: for events that did not resolve and decrease by one grade or more from the worst post-baseline severity as of the last recorded severity (i.e., severity did not subsequently worsen), then the date of improvement is the start date when the post-baseline grade becomes lower than the worst grade for the first time without any subsequent grade(s) equal to the worst grade.

Time to resolution is computed from start date of first treatment emergent episode of the event or start date of newly onset event after first dose of treatment drug to date of resolution.

Time to improvement is computed from start date of the worst grade of the event. Time to resolution /improvement will be summarized at the event level.

For summaries of events or summaries of patients with events ongoing at EOT, EOT is defined as the EOT visit or 30 days after the last dose of either study drug.

Time to onset of treatment-emergent adverse events is defined as time from the date of first dose to start date of first treatment emergent episode of the event or start date of newly onset event after first dose of treatment drug. In the analyses of time to onset by grade, the events should be excluded where the specified grade only occurs after a higher grade.

Peripheral Neuropathy

Peripheral Neuropathy (PN) is defined by the peripheral neuropathy MedDRA SMQ broad search. The incidence of PN at baseline will be summarized. The incidence of treatment-emergent and treatment-related PN will each be summarized by preferred term and severity. The incidence of PN leading to treatment discontinuation or requiring dose modification will be summarized. Time to onset, resolution, and improvement of PN events will be summarized.

Subjects with any event of treatment-emergent PN will be categorized into groups according to the following criteria:

- Resolution of all events
- At least 1 event resolved, but all other peripheral neuropathy events did not improve
- Improvement of at least one event
 - All events either improved or resolved
 - Some events improved, some events resolved and some events neither improved nor resolved
 - Some events improved but no events resolved
- No improvement or resolution of any events

The number of subjects will be summarized for the categories defined as above. The incidence of treatment-emergent motor neuropathy will be summarized by preferred term and severity. Time to resolution and improvement of motor neuropathy events will be summarized.

Infusion related reactions

Infusion related reactions (IRR) are defined as any event indicated as IRR by the investigator. The incidence of IRR will be summarized by preferred term and severity. The incidence of IRR leading to treatment discontinuation or requiring dose modification will be summarized for each infusional study drug component. The number of cycles of treatment to first onset of IRR will be summarized.

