### **7.6.1.3 Reporting Periods for Adverse Events and Serious Adverse Events**

The safety reporting period for all AEs and SAEs is from study Day 1 (predose) through the EOT visit or 30 days after the last brentuximab vedotin dose or 100 days after the last nivolumab dose, whichever is later. However, all study protocol-related AEs are to be recorded from the time of informed consent. All SAEs that occur after the safety reporting period and are considered study treatment-related in the opinion of the investigator should also be reported to the sponsor.

SAEs will be followed until significant changes return to baseline, the event stabilizes (recovering/resolving) or is no longer considered clinically significant by the investigator, or the patient dies or withdraws consent. All non-serious AEs will be followed through the safety reporting period. Certain non-serious AEs of interest may be followed until resolution, return to baseline, or study closure.

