6 STATISTICAL CONSIDERATIONS

6.1 General Principles

This is a phase 1/2 open label study with a formal statistical hypothesis for the primary efficacy endpoint of CR rate. The test of the primary endpoint will be at level $\alpha = 0.05$, using a 1-sided test. There are no formal pre-specified hypotheses associated with the primary safety objective, and no additional hypothesis tests of secondary endpoints.

Descriptive statistics (mean, median, standard deviation, minimum, maximum) will be used to describe continuous variables. Frequencies and percentages will be used to describe categorical variables. The median survival time will be estimated using the Kaplan-Meier method; the associated confidence interval (CI) will be calculated based on the complementary log-log transformation (Collett 1994). Unless otherwise specified, confidence intervals will be calculated at a two-sided 95% level.

Patients will be summarized overall and by dose regimen, unless otherwise specified in section 7. Additional summaries may be performed by selected patient characteristics and for subgroups of interest.

Any analysis not described in this plan will be considered exploratory, and will be documented in the clinical study report (CSR) as a post hoc analysis or a change to the planned analysis.

To comply with regulatory electronic submission guidelines, listings of all clinical data will be submitted as electronic data sets. To facilitate data review for the study report, only pertinent data listings will be created and attached to the appendix of the CSR. All statistical output will be produced using SAS®, version 9.4 or more recent. Other statistical software, if used, will be described in the CSR.

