6.5 Handling of Dropouts and Missing Data

With the exception of AE dates, missing data will not be imputed.

AE dates will be imputed for the purpose of calculating duration of events and treatmentemergent status (see Appendix A for imputation details and Appendix B for treatmentemergent definition). Censoring for time-to-event endpoints will be described in Section 7.5. with each planned analysis, as applicable.

Patients whose disease response cannot be assessed will be scored as non-responders for calculating the CR rate and ORR. Patients with missing values of a variable other than response endpoints (CR and ORR) and time-to-event endpoints (PFS and OS) will be excluded from the analysis of that endpoint unless otherwise specified.

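### Neuropathy time-to-resolution and time-to-improvement medians are conditional on outcome with no censoring rule, so resolution times are biased short by an amount that depends on follow-up

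*SAP*

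**What the plan says.** SAP 7.6.1.1 sets the dates. For events starting after first dose, "if event outcome is 'recovered/resolved' or 'recovered/resolved with sequelae', then the date of resolution is the event end date". Events present at baseline count as resolved when severity is back to baseline or lower. "Time to resolution is computed from start date of first treatment emergent episode of the event" (or from the start of a newly occurring event) to that date. Improvement is a separate class: "For events that are not resolved, improvement is defined as decrease by at least one grade from worst grade", timed from the start of the worst grade. Then: "Time to resolution /improvement will be summarized at the event level".

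Under its Peripheral Neuropathy heading the same section adds: "Time to onset, resolution, and improvement of PN events will be summarized". It also plans time to resolution and improvement for motor neuropathy, and it sorts patients with treatment-emergent PN into outcome groups, one of which is no improvement or resolution at all.

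Two general rules bear on the method. SAP 6.1: "Descriptive statistics (mean, median, standard deviation, minimum, maximum) will be used to describe continuous variables". SAP 6.5 sends censoring rules to Section 7.5, which covers efficacy, and says that patients with missing values of other variables "will be excluded from the analysis of that endpoint unless otherwise specified".

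On follow-up, Protocol 7.6.1.3 says "All non-serious AEs will be followed through the safety reporting period". That period normally ends 100 days after the last nivolumab dose. The sentence after it allows certain non-serious AEs of interest to be followed until resolution, return to baseline or study closure.

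**The concern.** A median taken only over events that resolved before follow-up ended leaves out the slow ones. It shortens as follow-up shortens, whatever the true course of the neuropathy. Time to improvement has a further selection: an event that falls from Grade 3 to Grade 1 and later clears drops out of the improvement summary because it resolved. Neither summary describes all neuropathy events.

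Safety is a primary objective, and the protocol names peripheral neuropathy as a commonly observed brentuximab vedotin toxicity (Protocol 3.1.4). A short median time to resolution is the figure a reader would carry away about reversibility. Protocol 2.3 also lists a comparison of safety between staggered and same-day dosing. A median that tracks length of follow-up would differ between parts followed for different times even if resolution were the same.

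**Working it through.** The documents give no figure for time to resolution, so there is none to reproduce.

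**Which events get a time.** By status at last assessment:

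| Status | Time to resolution | Time to improvement |
|---|---|---|
| Resolved | yes | no |
| Unresolved, at least one grade below worst | no | yes |
| Unresolved, still at worst grade | no | no |

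SAP Appendix A agrees: it imputes no end date when the last outcome is recovering, not recovered, unknown or blank. By contrast, the two duration endpoints, both PFS endpoints and OS in SAP 7.5 each have Kaplan-Meier estimation and a stated censoring rule.

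**Inputs from the documents.** Four 21-day cycles put the last planned dose on day 1 + 3 × 21 = 64. The default AE cutoff is day 64 + 100 = 164, which is 163/7 = 23.3 weeks after Day 1.

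**Inputs assumed (not in the documents).** True median time to resolution m of 8 or 39 weeks; exponential resolution, with Weibull shapes as sensitivity; onset uniform over the windows shown below.

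**Fixed follow-up F after onset.** Share resolved p = 1 − 2^(−F/m). Resolved-only median t = −m × log2(1 − p/2). With F = 100/7 = 14.3 weeks:
- m = 8: p = 0.71, t = −8 × log2(0.645) = 5.1 weeks.
- m = 39: p = 0.22, t = −39 × log2(0.888) = 6.7 weeks.

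**Staggered onset, cutoff at week 23.3 (simulation).** Resolved-only median in weeks, with percent resolved:

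| Onset window (weeks) | True 8 | True 39 |
|---|---|---|
| 0–9 | 5.9 (80%) | 8.6 (28%) |
| 0–12 | 5.6 (77%) | 7.9 (26%) |
| 3–12 | 5.3 (74%) | 7.3 (24%) |
| 6–12 | 5.0 (71%) | 6.7 (22%) |
| 0–23.3 | 4.3 (57%) | 6.2 (18%) |

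With Weibull shapes 0.7 to 2 (onset weeks 0–12) the ranges are 3.9 to 7.6 and 5.5 to 12.2 weeks.

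**Longer follow-up (onset weeks 0–12).** True 8 against true 39 weeks:
- 26 weeks beyond the default cutoff: 7.7 against 17.6.
- 52 weeks beyond: 8.0 against 24.6. Across the onset windows above, true 39 gives about 23 to 25.
- 156 weeks beyond: 8.0 against 36.6.

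**Dependence on follow-up alone.** For one true median of 26 weeks, the formula gives 10.8 weeks at F = 26 and 17.6 weeks at F = 52.

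**Kaplan-Meier with unresolved events censored** (30 events, onset weeks 0–12, cutoff week 23.3). True 8: typical Kaplan-Meier median 8.4 weeks, against 5.6 resolved-only. True 39: median not reached in 90% of simulated trials, against 8.0 weeks resolved-only.

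Time to improvement was not simulated. Omitting events that have not yet improved shortens it in the same way; omitting resolved events adds a selection whose direction the documents do not settle.

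**The case against.** **Follow-up may be longer than the default.** Protocol 7.6.1.3 allows AEs of interest to be followed to resolution or study closure, neuropathy is an obvious candidate, and long-term visits run to 36 months. A reader might infer that the reported median would sit at 5 to 7 weeks whatever the truth. The documents do not support that: it needs the default cutoff, exponential times and particular onset assumptions, and with a year more the medians separate. What remains is that the permission is optional and names no event, Protocol 6.7 lists no AE recording at long-term visits, and a true 39 weeks is still understated after an extra year.

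**Non-resolution is reported elsewhere.** A reader might infer that the plan hides lasting neuropathy. It does not: PN patients are counted by outcome, and the section provides for events ongoing at end of treatment. These counts stand beside the medians but are not timed and do not change them.

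**The SAP never says resolved events only.** That is correct. The exclusion rule in 6.5 concerns patients rather than AE records, and its list of time-to-event endpoints is not exhaustive, since the duration endpoints are missing from it yet are analysed by Kaplan-Meier. The inference rests on the date definitions and the absence of any rule for unresolved events.

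**Scope and weight.** A reader might extend the point to all AEs of special importance. The section specifies time to resolution only for PN and motor neuropathy; for infusion reactions it plans cycles to first onset. Nor is time to resolution part of the primary safety endpoint, which is type, incidence, severity, seriousness and relatedness. Separating resolved from improved is also a reasonable choice for classifying patients; the difficulty arises only when it is used to select events for a time summary.

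**Conclusion.** The point holds for PN and motor neuropathy. As defined, both medians are conditional on outcome, and time to resolution is biased short. Under the default cutoff and exponential resolution, true medians of 8 and 39 weeks would be reported as about 4 to 6 and 6 to 9 weeks, which hardly distinguishes quick recovery from slow. With about one more year they become about 8 and 24 weeks: distinguishable, with the slow one still understated. The true medians, the distribution and the onset windows are assumptions; only the dosing and reporting windows come from the documents. This concerns a descriptive safety summary and does not touch the CR-rate test or the incidence tables.

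**What to change.** In SAP 7.6.1.1:

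- **Time to resolution.** Estimate from event onset by Kaplan-Meier over all treatment-emergent PN and motor neuropathy events, with unresolved events censored at the last AE assessment or data cutoff. Treat death as a competing event (cumulative incidence), or censor at death and state the number.
- **Time to first improvement or resolution.** Estimate over all events from the start of the worst grade, so that resolved events are included and there is a single time origin.
- **Reporting.** Give the median or not reached, percent resolved at fixed times and the number unresolved. Confidence intervals should allow for several events per patient, or the analysis should use one event per patient.
- **Current medians.** Keep them only if labelled as among resolved events, or among improved but unresolved events, with n/N.

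The cost is SAP wording and one extra programme, with no change at sites. The reported times will be less favourable, and some medians may not be reached.

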7.6.1.2 Clinical Laboratory Parameters

Clinical laboratory data (hematology, serum chemistry and coagulation panel) will be summarized by treatment group. All laboratory results through the end of treatment visit will be presented in standardized units. Both observed data and changes from baseline for chemistry and hematology will be summarized with descriptive statistics. In addition, laboratory data will be summarized by the worst post-baseline NCI CTCAE grade for each parameter.

Laboratory results and NCI CTCAE grades for hematology and serum chemistry will be presented in data listings. Normal ranges will be documented and out-of-range values will be flagged.

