### **4.1 Inclusion Criteria**

1. Documented histopathological diagnosis of classical HL, excluding nodular lymphocyte-predominant Hodgkin lymphoma (NLPHL)
2. Patients must have biopsy-proven (see Section 6.2) relapsed or refractory disease after failure of standard frontline chemotherapy for the treatment of classical HL
  - Relapsed disease is defined as achieving a CR to frontline therapy but then progressing 3 months or more after completing frontline therapy
  - Refractory disease is defined as never achieving a CR to frontline therapy or having a CR but then progressing within 3 months of completing frontline therapy
3. Patients must have fluorodeoxyglucose positron emission tomography- (FDG-PET) avid and bidimensional measureable disease of at least 1.5 cm in longest axis as documented by radiographic technique (spiral computed tomography [CT] preferred)
4. Patients must have confirmation of diffusing capacity of the lung for carbon monoxide (DLCO) over 60% (adjusted for hemoglobin) by a pulmonary function test
5. Age 18 years and older
6. An Eastern Cooperative Oncology Group (ECOG) performance status score of 0–1
7. Patients must be considered eligible to undergo autologous stem cell transplant
8. Patients must have the following required baseline laboratory data:
  - Absolute neutrophil count (ANC)  $\geq 1000/\mu\text{L}$
  - Platelet count  $\geq 50,000/\mu\text{L}$  (no platelet transfusions for prior 14 days)
  - Hemoglobin  $\geq 8.5 \text{ g/dL}$  (no red blood cell [RBC] transfusions for prior 7 days)
  - Serum bilirubin  $\leq 1.5 \times$  upper limit of normal (ULN) (except patients with Gilbert Syndrome, who can have total bilirubin  $< 3.0 \times$  ULN)
  - Alanine aminotransferase (ALT) and aspartate aminotransferase (AST)  $\leq 2.5 \times$  ULN

- Calculated creatinine clearance of  $\geq 30$  mL/min

9. Females of childbearing potential must have a negative serum or urine beta human chorionic gonadotropin ( $\beta$ -hCG) pregnancy test result within 7 days prior to the first dose of brentuximab vedotin. Females with false positive results and documented verification that the patient is not pregnant are eligible for participation. Females of non-childbearing potential are those who are postmenopausal greater than 1 year or who have had a bilateral tubal ligation or hysterectomy

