### **5.6.3 Management of Immune-Adverse Events**

Immuno-oncology agents are associated with AEs that can differ in severity and duration from AEs caused by other therapeutic classes. Nivolumab is considered an immuno-oncology agent in this protocol. Early recognition and management of AEs associated with immune-oncology agents may mitigate severe toxicity. The following groups of AEs should be managed per the algorithms found in Appendix 3 of the nivolumab Investigator's Brochure:

- Gastrointestinal
- Renal
- Pulmonary
- Hepatic, with the following exceptions:

- Patients with a baseline LFT level in the Grade 1 range (AST or ALT >ULN to 3.0 x ULN and/or total bilirubin >ULN to 1.5 x ULN) should be managed by AE Grade-specified algorithms as applied to the absolute increase in AE Grade level above base line. For example, management of a Grade 3 AST elevation for a patient who had a baseline AST level in the Grade 1 range would be per the Grade 2 algorithm.
- Endocrinopathy
- Skin
- Neurological

See Section [5.5.2](#) for allowed high-dose corticosteroid treatment.

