### **7.6.2 Clinical Laboratory Tests**

Samples will be drawn for local and central labs. Local laboratory testing will be used for evaluating safety and making clinical decisions. The following laboratory assessments will be performed by both the local and central lab to evaluate safety at scheduled timepoints (see [Appendix A](#)) during the course of the study:

- The chemistry panel is to include the following tests: albumin, alkaline phosphatase, ALT, AST, blood urea nitrogen, calcium, creatinine, chloride, lactate dehydrogenase, phosphorus, potassium, sodium, total bilirubin, amylase, lipase, and gamma-glutamyl transpeptidase, serum glucose, and uric acid. Additionally, TSH, free T3, and free T4 must also be tested at Cycle 1, Cycle 3, and EOT.
- The CBC with differential is to include the following tests: white blood cell count with five-part differential (neutrophils, lymphocytes, monocytes, eosinophils, and basophils), platelet count, RBC count, bands and blasts, hemoglobin, and hematocrit.

The following additional laboratory assessment(s) will be performed by local laboratories at the designated timepoints (see [Appendix A](#)):

- Hepatitis B and C serologies; if hepatitis C serology is positive, HCV RNA test by PCR is required to confirm
- Epstein-Barr virus serology
- A serum or urine  $\beta$ -hCG pregnancy test for females of childbearing potential

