3 STUDY ENDPOINTS

3.1 Primary Endpoints

- Type, incidence, severity, seriousness, and relatedness of adverse events and laboratory abnormalities
- Complete remission rate following the completion of study treatment

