APPENDIX B: DEFINITION OF THE TERM "TREATMENT-EMERGENT" WITH RESPECT TO AE CLASSIFICATION

The algorithm below should be used to determine whether an adverse event (AE) is classified as a treatment-emergent adverse event (TEAE). A TEAE is defined as any AE which is newly occurring or worsening in severity, where newly occurring means that the AE was not present at baseline. For ease of reading, both pre-existing conditions and AEs will be referred to as AEs for the remainder of this document. AE dates should be imputed in accordance with the algorithm detailed in Appendix A. prior to determination of TEAE classification. Details of the TEAE classification are as follows:

- 1) Determine the first/earliest dose date of any study treatment (for combination studies this includes any component of the regimen)
- 2) **Baseline AEs:** classify an AE as a baseline AE if it satisfies both of criteria 1 and 2 below:
 - 1. The onset period field is: "started before the signing of informed consent"; or "started after consent but before the first dose of any study treatment"; or, the onset period field is missing and the AE start date is prior to the first dose date of any study drug (step 1, above).
 - 2. The stop date satisfies either of i or ii below:
 - i. The stop date is the same as or a later date than the first dose date of any study treatment
 - ii. The stop date is missing with outcome equal to
 - recovering/resolving (this outcome may or may not be associated with a date),
 or
 - not recovered/not resolved, or
 - unknown.
 - Note: if the AE has no outcome or stop date provided, the CRF data should be queried

Note: If the event ended on Day 1 (the date of first dose of any study drug) it will be considered a baseline event.

- 3) **Post-baseline AEs:** classify an AE as post-baseline if it meets either of criteria 1 or 2 below:
 - 1. The onset period of the AE is "started after the first dose of any study treatment"
 - 2. The onset period of the AE is missing and the AE start date is the same as or a later date than the first dose date of any study treatment
- 4) Compare post-baseline AEs to baseline AEs using the lower level term (LLT) and determine classification. Note that classification may not be possible and the TEAE variable will be missing:
 - 1. Classify all baseline AEs as not treatment emergent (not TEAEs).

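### The laboratory grade table ignores baseline grade, so unchanged pre-existing abnormalities count in the primary safety endpoint

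*SAP*

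**What the plan says.** Both documents put laboratory abnormalities in the primary safety endpoint. The wording in SAP 3.1 is "Type, incidence, severity, seriousness, and relatedness of adverse events and laboratory abnormalities", and Protocol 2.4.1 matches it.

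SAP 7.6.1.2 plans three laboratory outputs:

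- Values: "Both observed data and changes from baseline for chemistry and hematology will be summarized with descriptive statistics".
- Grades: "laboratory data will be summarized by the worst post-baseline NCI CTCAE grade for each parameter".
- Listings: "Laboratory results and NCI CTCAE grades for hematology and serum chemistry will be presented in data listings", with out-of-range flags.

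Protocol 9.3.8.4 adds only optional summaries of values and changes, and graded listings. Neither document plans a shift table, or a rule for when a laboratory grade is new or worse than baseline.

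Adverse events are treated differently. SAP Appendix B states: "A TEAE is defined as any AE which is newly occurring or worsening in severity". It then requires the post-baseline grade to exceed the baseline grade of the matching term.

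**The concern.** Patients can start treatment with graded abnormalities, and the protocol expects this. Inclusion criterion 8 ("Patients must have the following required baseline laboratory data") sets limits that lie outside the normal range for several tests. Protocol 5.6.3 has a separate management rule for "Patients with a baseline LFT level in the Grade 1 range", and Protocol 5.3.4.3 likewise distinguishes normal from Grade 1 baseline liver tests. So liver tests are read against baseline in patient care but not in the grade table.

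The adverse event route does not close the gap. Protocol 7.6.1.1 generally keeps a laboratory value off the adverse event form unless it has symptoms, needs intervention, becomes serious, or affects treatment or study participation. For everything else, the worst-grade table is the only planned summary of how many patients had an abnormality and how severe it was.

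Two readings of the trial are at stake. One is the incidence of laboratory abnormalities under the combination, which would mix carried-in abnormalities with new ones. The other is the descriptive comparison of staggered with same-day dosing, a protocol objective (section 2.3). The parts enrol one after another without randomisation, and Part 3 admits some patients with earlier brentuximab vedotin whom Parts 1 and 2 exclude. Baseline laboratory status could differ between regimens, and the table would show that as a difference in laboratory abnormalities.

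**Working it through.** **The plan's own safety figure.** SAP 6.2 gives a 94% chance of seeing at least one event with a true rate of 5% in 55 patients: 1 - (1 - 0.05)^55 = 0.9405. It reproduces and does not depend on this point.

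**Can an unchanged abnormality be counted?**

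- Entry limit for ALT and AST: up to 2.5 x ULN (Protocol 4.1).
- Protocol range for baseline Grade 1: above ULN to 3 x ULN (Protocol 5.3.4.3).
- A patient at 2 x ULN before dosing and at every later visit is Grade 1 throughout. The worst post-baseline grade is 1, so the patient is counted although nothing changed. Under the Appendix B rule for adverse events the same course would not be treatment-emergent.

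**How high can a persisting liver grade be?** In the protocol's ranges, Grade 3 starts above 5 x ULN for ALT/AST and above 3 x ULN for bilirubin. Entry limits are 2.5 x ULN for ALT/AST, 1.5 x ULN for bilirubin, and below 3.0 x ULN for bilirubin in Gilbert Syndrome. All lie below Grade 3, so an eligible value that does not change cannot enter the Grade 3 or higher counts. This uses the protocol's cut-offs, because the documents do not print the CTCAE ones. The amendment history notes that the two sets are not an exact match.

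**Other parameters.** Criterion 8 sets no limit for lymphocytes, amylase, lipase or electrolytes. The documents give no baseline distribution for them, so no size can be derived.

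**Illustration of size.** The documents give none of these inputs, so all three are assumptions:

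- t = share of all patients with a truly new or worsened grade
- b = share with a graded abnormality at baseline
- s = share of those abnormalities still present after baseline

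With t independent of baseline status, the share shown by the worst-grade table is t + (1 - t) x b x s. The share with a new or worsened grade is t.

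With t = 10% (5.5 of 55 patients):

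| b | s = 100% | s = 50% |
|---|---|---|
| 10% | 0.10 + 0.90 x 0.10 = 19.0% | 0.10 + 0.90 x 0.05 = 14.5% |
| 20% | 0.10 + 0.90 x 0.20 = 28.0% | 0.10 + 0.90 x 0.10 = 19.0% |
| 30% | 0.10 + 0.90 x 0.30 = 37.0% | 0.10 + 0.90 x 0.15 = 23.5% |

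Over a wider grid (t 5% to 20%, b 5% to 30%, s 50% to 100%), the ratio of tabulated to new-or-worsened incidence runs from 0.22 / 0.20 = 1.1 to 0.335 / 0.05 = 6.7.

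**Effect on the regimen comparison.** If t = 10% under both schedules but b is 10% in one and 30% in the other, the table shows 19% against 37% at full persistence (18 points apart), or 14.5% against 23.5% at half (9 points apart). The true difference is zero in both cases.

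**The case against.** The best defence is that the table does what its label says. It reports post-baseline grades and does not call them treatment-emergent or drug-related. A reader might infer that the SAP attributes carried-in abnormalities to treatment, and it does not say so. The wording stands, but a post-baseline incidence within a primary safety endpoint is easily read that way, and no other table corrects the reading.

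Second, baseline is not ignored. Changes from baseline in values are summarised, and listings allow patient-level checks. That is true, but average changes in values do not show how many patients moved up a grade, and a listing is not an incidence summary.

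Third, laboratory abnormalities with clinical consequences are recorded as adverse events and so pass through Appendix B. This stands and narrows the gap to the remainder.

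Two stronger readings are tempting and are not supported:

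- **Inflated severe toxicity.** For ALT, AST and bilirubin the entry limits rule it out under the protocol's ranges. For lymphocytes and other parameters without a limit it is possible, but the documents give nothing to show that it occurs or how often.
- **The worse of two laboratories.** Protocol 7.6.2 says that "The following laboratory assessments will be performed by both the local and central lab to evaluate safety", and a reader might infer that the worst grade is taken over both sets of results. SAP 7.6.1.2 does not say that they are pooled, and the same protocol section assigns safety evaluation to local testing. This point does not rest on it.

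**Conclusion.** The point holds as a limited one. The planned grade table counts unchanged pre-existing abnormalities, nothing else in either document separates them from new or worsened grades, and the table feeds a primary safety endpoint. For ALT, AST and bilirubin the effect is confined to grades below 3. For parameters without an entry limit the size is unknown.

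The 19% to 37% and 14.5% to 23.5% ranges show how the rule behaves under assumed inputs. They are not estimates for this trial, and a reader should not take them as the expected inflation. The distortion of the staggered versus same-day comparison is conditional on unequal baseline status, which the documents neither show nor exclude.

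Safety has no formal hypothesis (SAP 6.1), so no error rate, power or decision rule is affected. The consequence is a descriptive incidence that is harder to interpret than it needs to be.

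**What to change.** In SAP 7.6.1.2:

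1. Add a shift table for each graded parameter, with baseline grade in rows and worst post-baseline grade in columns, by regimen and overall. Give missing baseline its own row, and show parameters graded in both directions separately for high and low.
2. Report the number and percentage of patients whose worst post-baseline grade exceeds their baseline grade, using the baseline already defined in SAP 6.4.
3. Keep the existing worst-grade table alongside.

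The cost is a few lines of SAP text and standard programming. Baseline chemistry and blood counts are already collected, so no visit, sample or site procedure changes, and the hypothesis test and sample size are untouched.
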